9.6 Efficacy Subgroup Analyses

Subgroup analysis will be performed for the primary efficacy endpoint for the subgroups listed in Table 3 below using ITT2. Point estimate and 95% CI for each treatment group as well as point estimate and 95% CI for treatment differences between risankizumab 1200 mg IV and placebo groups will be presented. The NRI-MI approach will be used for missing data handling. No p-value will be provided. If any of the resulting subgroups except for age, sex and race has fewer than 10% of the planned study size, the subgroup analyses for that category will not be presented.

Table 3. Subgroups for Efficacy Analysis

Subgroup Factor	Categories
Age	[18, 40), [40, 65), ≥ 65
Sex	Male or Female
Baseline weight	< 60 kg or ≥ 60 kg
Race	White or non-White
Geographic Region	North America, South/Central America, Western Europe, Eastern Europe, Asia, Other
Baseline corticosteroid use	Yes or No
Baseline immunosuppressant use	Yes or No
Baseline Adapted Mayo Score	≤ 7 or > 7
Baseline Partial Adapted Mayo Score	≤ 4 or > 4
Prior exposure to anti-TNF for UC for non-Advanced Therapy-IR population	Yes or No
Number of prior failed anti-TNF for UC for Advanced Therapy -IR population	0, 1, 2, > 2
Prior exposure to advanced therapy	0, 1, > 1
Number of prior failed advanced therapies	0 (Non-Advanced Therapy -IR population), ≥ 1 (Advanced Therapy -IR population) (Then analyze 1, 2, > 2 within Advanced Therapy -IR population)
Presence of pancolitis at Baseline	Yes or No
Disease Duration at Baseline	\leq median or $>$ median
Disease Duration at Baseline	\leq 3 years or $>$ 3 years
Baseline hs-CRP	\leq median or $>$ median
Baseline hs-CRP	\leq 5 mg/L or $>$ 5 mg/L
Baseline Albumin	\leq median or $>$ median
Baseline Calprotectin	\leq median or $>$ median
Baseline Calprotectin	\leq 250 mg/kg or $>$ 250 mg/kg

All the secondary efficacy endpoints will be analyzed in the Advanced Therapy-IR and non-Advanced Therapy -IR subgroups in the ITT2 population.

In addition, point estimate of response rate will be summarized for primary endpoint for the following subgroups based on ITT2 population using NRI-MI for risankizumab treatment group (risankizumab 1200 mg IV):

- Treatment Emergent Anti-Drug Antibodies (ADA+, ADA-)
- Treatment Emergent NAb status (NAb+, NAb-)

10.0 Safety Analyses

10.1 General Considerations

Safety analysis will be performed on the safety populations in Induction Period 1 (SA2 population) and Induction Period 2 (SA2_P2 population) in Sub-Study 2. Safety summaries will be presented by treatment group, including a total group for all subjects on active study drug for SA2_P2. In addition, safety analysis will be provided for all Risankizumab treated safety population (SA2_ALL population) combined as one group.

For the safety analysis, subjects are assigned to a treatment group based on the treatment actually received, regardless of the treatment randomized.

The standard safety analyses will include reporting of adverse events (AEs), Areas of Safety Interest (ASIs), laboratory, and vital signs measurements. Frequency tables of subjects with treatment-emergent adverse events (TEAEs) by system organ class (SOC) and by preferred term (PT) as in the Medical Dictionary for Regulatory Activities (MedDRA) dictionary will be provided by treatment group. All continuous laboratory parameters and vital signs variables at each visit will also be summarized by actual treatment group. Frequency tables of subjects meeting criteria for potentially clinically significant vital sign values and for potentially clinically significant laboratory values will be provided by treatment group.

Missing safety data will not be imputed.

Baseline for laboratory and vital signs

For SA2 population, the baseline value is defined as the last available measurement before study drug administration for each subject. For SA2_P2 and SA2_ALL populations, the baseline value is defined as the last available measurement on or before first dose of risankizumab.

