Endoscopy and efficacy evaluation will occur at Week 12. Subjects in Sub-Study 2 who achieve clinical response per Adapted Mayo score (locally read Mayo endoscopic sub score) after completion of the 12-week Induction Period 1 will be enrolled into maintenance Study M16-066. Subjects who do not achieve clinical response at Week 12, may be eligible to enter a blinded risankizumab treatment in Induction Period 2 as specified below.

Subjects are not eligible to enter Induction Period 2 until the Week 12 endoscopy has been completed, except in case of COVID-19 pandemic restrictions or geo-political conflict in Ukraine and surrounding impacted regions:

If endoscopy cannot be performed at Week 12 due to COVID-19 pandemic restrictions or geo-political conflict in Ukraine and surrounding impacted regions, clinical response will be calculated using the Partial Adapted Mayo score.

Subjects with missing endoscopy due to COVID-19 pandemic restrictions or geo-political conflict in Ukraine and surrounding impacted regions and achieve clinical response per

Partial Adapted Mayo score at Week 12 may be eligible to enroll in Study M16-066 Sub-Study 3, which is an open-label long term extension study to evaluate long-term safety of risankizumab. Subjects who do not achieve clinical response at Week 12, may be eligible to enter a blinded risankizumab treatment in Induction Period 2 as specified below.

Sub-Study 2 Induction Period 2:

At Week 12, subjects who do not achieve clinical response will be randomized by Interactive Response Technologies (IRT) to Induction Period 2, a double-blind, double dummy 12-week treatment period to evaluate reinduction with risankizumab versus starting maintenance dosing on clinical response status.

[figure not shown]
Subjects who received IV risankizumab will be randomized 1:1:1 to:

- Group 1: Risankizumab 1200 mg IV Weeks 12, 16, and 20
- Group 2: Risankizumab 360 mg SC Weeks 12, and 20
- Group 3: Risankizumab 180 mg SC Weeks 12, and 20

Subjects who received placebo induction treatment will receive:

- Group 4: Risankizumab 1200 mg IV Weeks 12, 16, and 20

The schematic of the Induction Period 2 is shown in [Figure 2](#).

Figure 2. Study Schematic of Induction Period 2

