4.0 Analysis Populations

The following population sets will be used for the statistical analyses:

Intent-to-Treat Population

Sub-Study 2 Induction Period 1:

ITT2 includes all randomized subjects who received at least one dose of study drug during Induction Period 1. The **ITT2** will be used for all efficacy analysis, and demographic and baseline characteristics summary for Induction Period 1. Subjects will be included in the analysis according to the treatment groups that they are randomized to.

Sub-Study 2 Induction Period 2:

ITT2_P2 includes all subjects who received at least one dose of risankizumab during Induction Period 2 from Sub-Study 2. Subjects will be included in the analysis according to the treatment groups that they are re-randomized to the Induction Period 2 and the subjects who received placebo induction treatment during 12-Week Induction Period 1 and entered the Induction Period 2 will be also included (denoted as placebo/risankizumab). This analysis population will be used for efficacy analysis in Induction Period 2.

Safety Analysis Set

The safety analysis will be based on the corresponding safety analysis sets. Subjects will be analyzed in a treatment group based on the actual treatment received.

Sub-Study 2 – Induction Period 1

SA2 consists of all subjects who received at least one dose of study drug during Induction Period 1 in Sub-Study 2.

Sub-Study 2 Induction Period 2:

SA2_P2 consists of all subjects who received at least one dose of risankizumab during the Induction Period 2 after Week 12 in Sub-Study 2.

All Risankizumab:

SA2_ALL includes all subjects who received at least one dose of risankizumab any time during the Sub-Study 2.

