10.2.1 Treatment-Emergent Adverse Events

The Treatment-Emergent Adverse Events (TEAEs) for SA2, SA2_P2 and the SA2_ALL populations are defined as follows:

Induction Period 1 (SA2 population):

TEAEs for Induction Period 1 are defined as events that begin either on or after the first dose of the study drug in Induction Period 1 and

- before first dose of study drug in Induction Period 2 if the subject is enrolled into Induction Period 2 or
- before first dose of study drug in the Maintenance Study (M16-066) if the subject is enrolled into the Maintenance Study (M16-066) or
- within 140 days after the last dose administration of the study drug for subjects who are not enrolled in Induction Period 2 and do not participate in the Maintenance Study (M16-066); or for subjects who are responders in Induction Period 1 but do not participate in the Maintenance Study (M16-066).

Induction Period 2 (SA2_P2 population):

TEAEs for Induction Period 2 are defined as events that begin either on or after the first dose of risankizumab in Induction Period 2 and

- before first dose of study drug in the Maintenance Study if the subject is enrolled into the Maintenance Study (M16-066) or
- within 140 days after the last dose administration of the study drug for subjects who do not participate in the Maintenance Study (M16-066).

SA2_ALL population:

TEAEs are defined as events that begin either on or after the first dose of risankizumab in either Induction Period 1 or Induction Period 2 and

- before first dose of study drug in the Maintenance Study (M16-066) if the subject is enrolled into the Maintenance Study (M16-066) or
- within 140 days after the last dose of risankizumab in this study for subjects who do not participate in the Maintenance Study (M16-066).

Events where the onset date is the same as the study drug start date are assumed to be treatment-emergent, unless the study drug start time and the adverse event start time are collected and the adverse event start time is prior to the study drug start time. If an incomplete onset date was collected for an adverse event, the event will be assumed to be treatment-emergent unless there is other evidence that confirms that the event was not treatment-emergent (e.g., the event end date was prior to the study drug start date).

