10.3 Analysis of Laboratory Data

Data collected from central and local laboratories, including additional laboratory testing due to an SAE, will be used in all analyses, except for Baseline where SAE-related laboratory assessments on or before the first dose of study drug will be excluded. The clinical laboratory tests defined in the protocol (e.g., hematology and clinical chemistry) will be summarized.

Analysis of Quantitative Laboratory Parameters

For SA2 and SA2_P2 populations, each laboratory variable will be summarized for all time points (starting with Baseline) with the number of non-missing observations, mean and standard deviation, median, minimum and maximum. Mean change from baseline to each applicable post-baseline visit will be summarized for selected laboratory variables, with the number of observations, baseline mean, and visit mean. The change from baseline mean, standard error, and 95% confidence interval will be presented for the mean change from baseline within each treatment group. In addition, for SA2_P2 populations, each laboratory variable will be summarized for all time points (starting with Induction

Period 2 baseline referring to the last available measurement before first dose in Induction Period 2) with the number of non-missing observations, mean and standard deviation, median, minimum and maximum. Mean change from Induction Period 2 baseline to each applicable post-baseline visit will be summarized for selected laboratory variables, with the number of observations, baseline mean, and visit mean. The change from Induction Period 2 baseline mean, standard error, and 95% confidence interval will be presented for the mean change from Induction Period 2 baseline within each treatment group.

For SA2 population, treatment group differences between Risankizumab 1200 mg IV treatment group and placebo group for changes from Baseline will be analyzed using a one-way Analysis of Variance (ANOVA) model with treatment as a fixed factor and 95% CI for treatment difference will be presented for selected laboratory parameters.

Shift Table Analyses

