For SA2 and SA2_P2 populations, changes in laboratory parameters will be tabulated using shift tables either by NCI CTC criteria or categorized as low, normal, or high based on the normal ranges of the laboratory used for each sample. A shift table from baseline either to the worse value (based on NCI CTC criteria) during treatment or to minimum and maximum value (based on normal range), will be created. A similar shift table will be provided to summarize shifts from baseline to the final post-baseline value.

Potentially Clinically Significant Laboratory Values

For SA2, SA2_P2 and SA2_ALL populations, laboratory abnormalities meeting CTC criteria grade 3, grade 4 and \geq Grade 3 will be summarized, with a grade worsening compared to baseline.

Laboratory abnormalities will be evaluated based on Potentially Clinically Significant (PCS) criteria (). For each laboratory PCS criterion, the number and percentage of subjects who have a laboratory value meeting the criteria will be summarized. Listings will be provided to summarize subject-level laboratory data for subjects meeting PCS criteria.

Assessment of Liver Elevations

For SA2, SA2_P2 and SA2_ALL populations, the liver-specific laboratory tests include the serum glutamic pyruvic transaminase (SGPT/ALT), serum glutamic-oxaloacetic transaminase (SGOT/AST), alkaline phosphatase (ALP), and total bilirubin (TBL). The frequencies and percentages of subjects with post baseline liver specific function test values that meet the following criteria of potential clinical interest will be summarized by treatment group:

- $ALT \geq 3 \times ULN$
- $ALT \geq 5 \times ULN$
- $ALT \geq 10 \times ULN$
- $ALT \geq 20 \times ULN$
- $AST \geq 3 \times ULN$
- $AST \geq 5 \times ULN$
- $AST \geq 10 \times ULN$
- $AST \geq 20 \times ULN$
- $TBL \geq 2 \times ULN$
- $Alkaline\ phosphatase \geq 1.5 \times ULN$
- $(ALT\ and/or\ AST \geq 3 \times ULN)\ and\ (TBL \geq 1.5 \times ULN)$
- $(ALT\ and/or\ AST \geq 3 \times ULN)\ and\ (TBL \geq 2 \times ULN)$

where ULN is the upper limit of normal.

A listing of potentially clinically significant liver function laboratory values will be provided. The listing will include all subjects who met any of the following 4 criteria:

- $ALT \geq 3 \times ULN$, or
- $AST \geq 3 \times ULN$, or
- $Alkaline\ phosphatase \geq 1.5 \times ULN$, or
- $Total\ bilirubin \geq 1.5 \times ULN$.

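### In the Period 2 safety tables (SA2_P2) the laboratory and vital-sign baseline is Week 0 for the re-randomised arms but Week 12 for placebo/risankizumab, so identical abnormalities are counted differently by arm

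*SAP*

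**What the plan says.** All section numbers here refer to the Sub-Study 2 SAP unless the protocol is named.

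- **Population.** Section 4.0: "SA2_P2 consists of all subjects who received at least one dose of risankizumab during the Induction Period 2 after Week 12 in Sub-Study 2". It pools subjects from both Period 1 arms.
- **Who enters.** Section 2.2: "Subjects who received IV risankizumab will be randomized 1:1:1 to" one IV and two SC regimens; "Subjects who received placebo induction treatment will receive" IV risankizumab from Week 12.
- **Baselines.** Section 10.1, Period 1: "For SA2 population, the baseline value is defined as the last available measurement before study drug administration for each subject". Period 2: "For SA2_P2 and SA2_ALL populations, the baseline value is defined as the last available measurement on or before first dose of risankizumab". The same section asks for an SA2_P2 total column across the active groups.
- **Tables that use plain baseline.** Section 10.3 plans shift tables for SA2 and SA2_P2. For SA2, SA2_P2 and SA2_ALL it counts Grade 3 and Grade 4 values "with a grade worsening compared to baseline". The notes to Tables C-1 and C-2 in Appendix C require a higher CTC grade than at baseline for a laboratory PCS finding. Table C-3 requires a set change from Baseline for blood pressure, and section 10.4 applies it to SA2_P2.
- **A second baseline.** Section 10.3 also defines an Induction "Period 2 baseline referring to the last available measurement before first dose in Induction Period 2". Sections 10.3 and 10.4 use it only for additional descriptive and mean-change summaries.
- **Adverse events.** Section 10.2.1: "TEAEs for Induction Period 2 are defined as events that begin either on or after the first dose of risankizumab in Induction Period 2".

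**The concern.** The Period 2 tables place the placebo/risankizumab arm beside three arms with 12 weeks of earlier risankizumab. A reader will take a Grade 3 or PCS count in such a table as what happened in Period 2. For the re-randomised arms, however, the count measures change since Week 0. For placebo/risankizumab it measures change since Week 12.

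Three things are at stake:

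- The placebo/risankizumab column can look cleaner or worse than its neighbours with no true difference.
- The total column adds counts made on two different rules.
- Adverse-event and laboratory tables for the same period follow different conventions, because the adverse events are restricted to Period 2 onset. A persistent Period 1 abnormality in a re-randomised subject appears in the SA2 table and again in the SA2_P2 table.

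**Working it through.** The plan states no figure on this point, so there is none to reproduce. The check is one of logic, followed by an illustration with assumed rates.

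**Step 1: what first dose means in section 10.1.** It cannot reasonably mean the first Period 2 dose. The adverse-event definition adds the Period 2 qualifier explicitly, and the separate Induction Period 2 baseline would be redundant if section 10.1 already meant that. The SA2_P2 baseline is therefore the Week 0 value for re-randomised subjects and the last value up to Week 12 for placebo/risankizumab.

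**Step 2: apply the counting rule.** A subject counts if the worst grade is 3 or higher and exceeds the baseline grade. The SAP states no observation window for these SA2_P2 tables, so two are shown for the re-randomised arms.

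| Course of the abnormality | Re-randomised, Period 2 values only | Re-randomised, all values after Week 0 | Placebo/risankizumab | Every arm on Period 2 baseline and window |
|---|---|---|---|---|
| 1. Grade 3 starts in Period 1, persists at Week 12 and in Period 2 | counted | counted | not counted | not counted |
| 2. Grade 3 starts in Period 1, resolved by Week 12 | not counted | counted | not counted | not counted |
| 3. Grade 3 starts in Period 2 | counted | counted | counted | counted |
| 4. Grade 3 at Week 0, resolved at Week 12, recurs in Period 2 | not counted | not counted | counted | counted |

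Course 1 differs by arm under either window. Course 2 differs only if Period 1 visits are admitted. Course 4 runs in the opposite direction. On a common Period 2 baseline and window, every course is treated alike in every arm.

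**Step 3: illustration.** All rates are assumed, identical in both groups, with no subject in course 4 and no overlap between Period 1 and Period 2 onset. Let n = 2% be Period 2 onset, a = 1% to 5% Period 1 onset, and p = 25% to 75% the share of a that persists.

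- Placebo/risankizumab: 100 × n = 2.00 per 100.
- Re-randomised, Period 2 values only: 100 × (n + a × p). Lowest: 100 × (0.02 + 0.01 × 0.25) = 2.25. Highest: 100 × (0.02 + 0.05 × 0.75) = 5.75.
- Re-randomised, all values after Week 0: 100 × (n + a) = 3.00 to 7.00.
- Every arm on the Period 2 baseline and window: 2.00.

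In subjects, if 35% to 50% of the 644 risankizumab subjects enter Period 2 (also assumed), each re-randomised arm has 644 × 0.35 / 3 = 75 to 644 × 0.50 / 3 = 107. The carried-over excess a × p is then about 75 × 0.0025 = 0.2 to 107 × 0.0375 = 4.0 subjects per arm.

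**The case against.** Much can be said for the plan.

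- **Pre-exposure baseline.** It is a legitimate choice, because it shows worsening since the drug-naive state. Resetting at Week 12 would hide a Grade 3 value that arose on risankizumab in Period 1. SA2_ALL would not restore the by-arm view, since it is one combined group. This stands, and it is why the existing display should be kept rather than replaced.
- **Re-induction versus SC dosing.** A reader might infer that this randomised comparison is biased. It is not. All three arms received IV risankizumab in Period 1 and share the Week 0 baseline. Carried-over abnormalities fall on them equally in expectation, which leaves differences unchanged and at most pulls ratios towards one.
- **Liver monitoring.** A reader might infer that it is compromised. The dedicated liver table and the Hy's Law listing in section 10.3 use multiples of the upper limit of normal and require no worsening, so a placebo/risankizumab subject with a persisting elevation is still captured. Only the unstated window affects them.
- **Shift tables.** They exclude nobody. A Grade 3 value at Week 12 in a placebo subject appears as Grade 3 at baseline. What remains is that the reference time differs by arm.
- **Observation time.** A reader might infer up to 24 weeks of observation against 12. That is only one reading of a window the SAP leaves open.
- **Planned use.** The affected contrast is not randomised, and no laboratory or vital-sign treatment difference is planned for SA2_P2. Protocol sections 8.1.1.2 and 8.1.7 call the Period 2 analyses exploratory. Protocol section 5.4.1 withdraws subjects with certain abnormal results, which limits carry-over. Subject-level PCS listings also remain.

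These points narrow the problem. None removes the two counting rules in one Grade 3/4 or PCS table.

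**Conclusion.** The point holds for the SA2_P2 Grade 3/4 worsening table and the laboratory and vital-sign PCS tables, where identical courses are counted differently by arm, and for the total column that mixes both baselines. The shift tables are affected only through different reference times.

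The distortion can go either way: persistent Period 1 abnormalities inflate the re-randomised arms, while resolved and recurring ones are missed there. A fixed multiple, such as a doubled rate, is not supported. The documents give neither abnormality rates nor the share entering Period 2, so the figures above only illustrate their assumptions. The analyses are exploratory, so this is a reporting improvement worth making and does not threaten any confirmatory result.

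**What to change.** In sections 10.1, 10.3 and 10.4:

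1. Produce the SA2_P2 shift, Grade 3/4 worsening, laboratory PCS and vital-sign PCS tables on the Induction Period 2 baseline already defined, using only values after the first Period 2 dose.
2. State that same window for the SA2_P2 liver table and the Hy's Law listing.
3. Keep the pre-risankizumab baseline for SA2_ALL, and as a second by-arm SA2_P2 display labelled as change since first risankizumab dose. Shift tables are planned only for SA2 and SA2_P2, so without this display by-arm shifts since first exposure would be lost.

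The cost is SAP wording and one extra set of tables. No new data are needed: protocol Appendix C schedules chemistry, haematology and vital signs at Week 12, with study drug given after that day's assessments.

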10.2 Adverse Events

Adverse events (AEs) will be summarized and presented using primary MedDRA System Organ Classes (SOCs) and preferred terms (PTs) according to the version of the MedDRA coding dictionary used for the study at the time of database lock. The actual version of the MedDRA coding dictionary used will be noted in the AE tables and in the clinical study report. Specific adverse events will be counted once for each subject for calculating percentages, unless stated otherwise. In addition, if the same adverse event occurs multiple times within a subject, the highest severity and level of relationship to investigational product will be reported.

Summaries of AEs discussed in this section will be provided for SA2 and SA2_P2 population. For SA2_ALL population, exposure-adjusted AEs per 100 patient-years will be provided as described in Section 10.2.4. For exposure-adjusted event rate (EAER) calculation, the numerator will be the total number of AEs reported for the event (i.e., a subject can contribute more than one event to the numerator) and the denominator will be the total exposure time among subjects under the treatment group. The number of AEs reported (numerator), the total number of years of study drug exposure (denominator, calculated as total number of days exposed to study drug (i.e., last dose date – first dose date + 140 days) for all treated subjects divided by 365.25), and the exposure-adjusted AE event rate per 100 patient-years calculated as ([numerator (number of AEs)/denominator]) × 100 will be presented for each treatment group.

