For UC-related hospitalizations through Week 12, to consider Missing-Not-At-Random (MNAR) assumption due to different dropout rates between treatment groups, a supplementary analysis will be performed based on exposure adjusted occurrence of UC-related hospitalizations through Week 12. Exposure adjusted occurrence of UC-related hospitalization will be analyzed based on incidence rates. Incidence rates for hospitalization will be calculated as the number of patients with the respective event divided by the time at risk. For patients with an event during the study period, time at risk is the patient-years (PYs) from the first dose date to the first event before Week 12. For patients without an event during Period 1, time at risk is PYs from first dose date to the end of study follow-up period, where the follow-up period starts from the first dose date to the last dose date in Period 1+ 140 days if prematurely discontinues the study drug without entering Period 2 or M16-066, or the first dose date of Period 2 or M16-066 if enters Period 2 or M16-066, whichever occurs earlier. The event date is defined as the date of admission to the hospital for hospitalizations. The incidence rate difference, 95% CI and p-value are calculated to evaluate the statistical significance of the difference between risankizumab 1200 mg IV group and placebo group using normal approximation to Poisson distribution. The analysis will be based on the AO data.

The continuous secondary endpoints will be analyzed based on ITT2 by RTB-MI with MMRM (for endpoints with more than one post-baseline visits) or with ANCOVA (for endpoints with one post-baseline visit) and the corresponding analyses are specified in Section 9.2.2. The least square (LS) mean and 95% CI for each randomized treatment group and the LS mean treatment difference, the associated 95% CI and the p-value between risankizumab 1200 mg IV group and the placebo group will be provided. Considering unequal variances due to the unequal sample size in the two treatment groups (2:1 randomization), a sensitivity analysis will be performed for continuous secondary

endpoints with only a single post-baseline measure using an ANCOVA model that estimates variance by treatment group.

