10.2.2 Adverse Event Overview

For SA2 and SA2_P2 populations, an overview of AEs will be presented consisting of the number and percentage of subjects experiencing at least one event for each of the following AE categories:

- Any TEAE
- Any COVID-19 related TEAE
- Any TEAE related to study drug according to the investigator
- Any severe TEAE
- Any serious TEAE
- Any TEAE leading to discontinuation of study drug
- Any TEAE leading to death
- TEAE of Safety Interest (as defined in)

- All deaths
 - COVID-19 related deaths
 - Deaths occurring \leq 140 days after last dose of study drug
 - Deaths occurring $>$ 140 days after last dose of study drug.

Additional AEs may be considered for tabulation/summary based on recommendations from Clinical and Safety as deemed appropriate.

The point estimate and 95% CI (using normal approximation and separate group variance) will also be provided for the treatment difference in AE percentage between risankizumab group and the placebo group for analyses performed on SA2 population.

For SA2 and SA2_P2 populations, an overview of the ASI will be provided similarly and the categories of ASI are defined in [Appendix B](#).

In addition, for SA2 and SA2_P2 populations, an overview of AEs per 100 patient-years of study exposure and an overview of ASI per 100 patient-years of study exposure will be presented. The number of TEAEs reported, the total number of years of study drug exposure, and the TEAE rate per 100 patient-years will be presented. The point estimate and 95% CI will be provided for the treatment difference between risankizumab group and the placebo group.

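### Exposure-adjusted adverse event rates divide by 140 days after the last dose for every subject, although event counting stops at rollover, so the rates come out too low

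*SAP*

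**What the plan says.** All references are to the Sub-Study 2 SAP.

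- **Numerator (10.2).** For the exposure-adjusted event rate, "the numerator will be the total number of AEs reported for the event", and a subject may contribute more than one event. The overview in 10.2.2 specifies that the events are TEAEs.
- **Denominator (10.2).** Person-time is the "total number of days exposed to study drug (i.e., last dose date – first dose date + 140 days) for all treated subjects", converted to years. There is no cap at rollover.
- **Event window (10.2.1).** In SA2, counting ends "before first dose of study drug in Induction Period 2 if the subject is enrolled into Induction Period 2", or at the first M16-066 dose for subjects who go straight to maintenance. SA2_P2 and SA2_ALL also stop at the first M16-066 dose. The 140-day tail belongs to subjects who do not roll over; for SA2 it reads "within 140 days after the last dose administration of the study drug for subjects who are not enrolled in Induction Period 2" and who do not join M16-066, or who respond but do not join it.
- **Use of the rates.** Sections 10.2.2 and 10.2.4 apply rates per 100 patient-years to AEs and areas of safety interest in SA2 and SA2_P2. For the comparison of arms, "The point estimate and 95% CI will be provided for the treatment difference between risankizumab group and the placebo group". For the pooled set, "For SA2_ALL population, exposure-adjusted AEs per 100 patient-years will be provided as described in Section 10.2.4", and 10.2.4 refers back to 10.2 for the calculation.
- **Other person-time rules in the same SAP.** Section 6.1 caps duration of exposure at the first dose of the next period or of M16-066. For the UC-related hospitalization rate, 9.4.2 ends time at risk for subjects who roll over at "the first dose date of Period 2 or M16-066 if enters Period 2 or M16-066, whichever occurs earlier".

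**The concern.** A rate per patient-year is interpretable only if the denominator is the time during which an event would have entered the numerator. Here the two agree only for subjects who do not roll over. Rollover is the designed path out of Period 1: Week 12 responders go to M16-066, and non-responders may enter Period 2. The mismatch therefore affects most of SA2, always in the direction of lower rates.

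Three things are at stake.

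- The absolute SA2 rates and the planned risankizumab-minus-placebo rate difference with its 95% CI are too small.
- A placebo non-responder who enters Period 2 receives risankizumab from Week 12, yet the surplus days after that dose sit in the placebo denominator.
- In SA2_ALL these rates are the planned AE summary, covering serious TEAEs, deaths and areas of safety interest. No event rate with a matched window stands beside them.

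Section 10.2 also does not say whether first and last dose mean those of the analysis period or those of the whole sub-study.

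**Working it through.** The SAP states a formula but no rate or person-time total, so there is no planned figure to reproduce. The numerator is the same under either denominator. Hence

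reported rate / true rate = (days inside the TEAE window) / (last dose − first dose + 140), each summed over subjects.

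**Inputs from the documents.** Period 1 doses at Weeks 0, 4 and 8 (SAP 2.2), so first to last dose is 56 days. Period 2 doses at Weeks 12, 16 and 20 (IV) or 12 and 20 (SC), again 56 days. Rollover is nominally at Week 12 (day 84) or Week 24 (day 168). Planned arms are 644 and 322.

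**Assumed.** Rollover shares, which the documents do not give. First and last dose are read within the analysis period, and all subjects take every dose.

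**One SA2 rollover subject.** Denominator 56 + 140 = 196 days; window 84 days; 84/196 = 0.429. Surplus 196 − 84 = 112 days.

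**SA2 overall**, rollover share r: (84r + 196(1 − r))/196.

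| r | Ratio | Matched patient-years, risankizumab / placebo |
|---|---|---|
| 0.80 | 106.4/196 = 0.543 | 644 × 106.4/365.25 = 188; 322 × 106.4/365.25 = 94 |
| 0.95 | 89.6/196 = 0.457 | not needed below |
| 1.00 | 84/196 = 0.429 | 644 × 84/365.25 = 148; 322 × 84/365.25 = 74 |

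The SAP formula gives 644 × 196/365.25 = 346 and 322 × 196/365.25 = 173 patient-years. Corrected rates would be 1/0.543 = 1.84 to 1/0.429 = 2.33 times those planned.

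**Sensitivity.** If rollover falls on day 77, the range for r from 1.00 to 0.80 is 39% to 51%; on day 91 it is 46% to 57%. If the 20% who do not roll over had only one or two doses, the 80% figure becomes 51.5% or 52.9%.

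**Placebo person-time after risankizumab.** If 60% of placebo subjects enter Period 2: 322 × 0.6 × 112/365.25 = 59 of 173 patient-years (34%). If 80%: 79 of 173 (46%).

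**SA2_P2.** The same formula applies: 0.829 if 30% roll over at Week 24, 0.600 if 70% do.

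**SA2_ALL.** Window days over denominator days, by path:

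- risankizumab, rollover at Week 12: 84/196
- risankizumab, both periods then rollover: 168/280
- risankizumab, both periods without rollover: 280/280
- risankizumab, no Period 2 and no rollover: 196/196
- placebo entering Period 2: 84/196 with rollover, 196/196 without

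Assumptions: Week 12 response 40–70% on risankizumab and 20–50% on placebo, with all responders rolling over; 70–100% of non-responders entering Period 2, varied separately by arm; 30–70% of those rolling over at Week 24.

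- *Lowest:* response 70%/50%, Period 2 entry 100%/70%, Week 24 rollover 70%. Mean days per randomized risankizumab subject are 119.28 of 221.2. Placebo entrants are 35% of 322, with 117.6 of 196 days. Ratio (644 × 119.28 + 112.7 × 117.6)/(644 × 221.2 + 112.7 × 196) = 0.547.
- *Highest:* response 40%/20%, entry 70%/100%, rollover 30%. Means are 172.368 of 231.28. Placebo entrants are 80% of 322, with 162.4 of 196 days. Ratio (644 × 172.368 + 257.6 × 162.4)/(644 × 231.28 + 257.6 × 196) = 0.766.

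**Unequal rollover, illustrative only.** With 95% on risankizumab and 80% on placebo, equal true rates would be reported with ratio 0.457/0.543 = 0.84.

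**Other reading of last dose.** If it means the last dose in the sub-study, a Period 2 completer adds 140 + 140 = 280 days to SA2 against a window of 84: 84/280 = 0.30.

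**The case against.** The mismatch itself is hard to dispute, so the best case on the other side is that it matters little.

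- **Between-arm inference.** With equal rollover, the rate difference and its standard error shrink by the same factor. The rate ratio, and whether the interval excludes zero, do not change. This stands. What remains wrong is the absolute rates and the size of the difference. The 0.84 ratio needs unequal rollover, which no document supplies.
- **Percentages come first.** The SA2 overview also gives the difference in AE percentages, and both arms follow the same dosing schedule. This stands for SA2. It does not help SA2_ALL, where the planned AE summary is the exposure-adjusted rate.
- **The reader could repair the rate.** Event count and denominator are shown, 6.1 reports capped SA2_ALL exposure, and 10.2.6 allows a censored incidence rate for deaths and selected events. The repair is only approximate: 6.1 uses a 28- or 56-day tail for subjects who do not roll over, and the incidence rate is optional.
- **Section 9.4.2 is no perfect model.** It truncates at rollover, but event-free subjects who leave without rolling over accrue time beyond Week 12 for an endpoint counted through Week 12. This is right. It can be cited only for its treatment of rollover.
- **The percentages are conditional.** At 60% rollover the SA2 figure is (0.6 × 84 + 0.4 × 196)/196 = 66%. A smaller effect in SA2_P2 relies on fewer Week 24 rollovers, which is plausible because Week 24 non-responders are discontinued. At 100% Week 24 rollover SA2_P2 would also be at 43%, and SA2_ALL could fall about 2 points below SA2. The size depends on these shares; the direction does not.

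**Conclusion.** The concern holds. Following 10.2 as written gives event rates that are too low in every set containing subjects who roll over before last dose + 140 days. What follows from the planned schedule alone is the per-subject result: 196 denominator days against 84 at risk for a three-dose Week 12 rollover. The overall sizes rest on assumed rollover shares: 43–54% of true in SA2 at 100–80% rollover, 60–83% in SA2_P2 at 70–30%, and about 55–77% in SA2_ALL. Distortion between the arms arises only if rollover differs. Percentages of subjects with events in SA2 and SA2_P2, and all efficacy tests, are untouched.

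This should be corrected in the SAP and not left to programming. The formula is explicit and covers all treated subjects, so a programmer who truncates at rollover departs from the plan, and one who follows it produces the wrong rate. The 6.1 caps show that the SAP already treats exposure differently elsewhere.

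**What to change.** In SAP 10.2, define each subject's person-time as the TEAE window of that analysis set in 10.2.1:

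- **Start:** first Period 1 dose (SA2), first Period 2 dose (SA2_P2), first risankizumab dose (SA2_ALL).
- **End, if the subject rolls over:** the day before the dose that closes the window, without a 140-day cap. That dose is the first Period 2 or M16-066 dose for SA2, and the first M16-066 dose for SA2_P2 and SA2_ALL.
- **End, otherwise:** last applicable dose + 140 days.

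State that first and last dose are those of the analysis set. Align the rollover rule with 9.4.2. Because 6.1 defines exposure with different tails, call the 10.2 quantity time at risk, so that the two are not confused.

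The cost is a short text change and one revised derivation. All the dates needed are already used elsewhere in the SAP. The reported rates will be higher than under the current formula.
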